4.3.2. Analysis Methods

Subjects' status of spleen response and transfusion-independence will be listed for all eligible subjects.

Duration of response will be estimated using the Kaplan-Meier method. Approximate 95% confidence intervals for median duration of response will be computed using the formula proposed by Brookmeyer and Crowley. The same method will be applied for OS.

4.3.3. Other Measurements Collected

Time to response, transfusion, bone marrow, physical exam, spleen/liver assessment, and ultrasound result will be listed separately.

5. SAFETY

Safety will be analyzed using the incidence and severity of adverse events and laboratory tests based on the all treated analysis set.

5.1. Adverse Events

The verbatim terms used in the eCRF by investigators to identify AEs will be coded using the Medical Dictionary for Regulatory Activities (MedDRA). The severity of adverse events is assessed in National Cancer Institute (NCI) common terminology criteria for adverse events (CTCAE) Version 4.0.

Treatment-emergent AEs will be defined as those events that 1) occur on or after the first dose of study drug, through the treatment phase, and for 30 days following the last dose of study drug or until subsequent anti-cancer therapy if earlier; 2) any event that is considered study drug-related regardless of the start date of the event; or 3) any event that is present at baseline but worsens in severity or is subsequently considered drug-related by the investigator.

An overview summary table of treatment-emergent AEs will be provided, including drug related AEs, CTCAE grade ≥ 3 AEs, serious AEs, and deaths.

Treatment-emergent AEs will be summarized by system organ class and preferred terms. For each treatment-emergent adverse event, the percentage of subjects who experience at least 1 occurrence of the given event will be summarized. Tables will be sorted by frequency in incidence (the highest to lowest incidence) in the total column. The same summary will be provided for the treatment-emergent AEs with CTCAE grade ≥ 3 , treatment-emergent AEs considered related to study treatment, and serious treatment-emergent AEs.

A summary of the number of subjects who discontinued study treatment because of 1 or more AEs by system organ class and preferred term will be provided. This table includes AEs leading to discontinuation of study treatment for those subjects indicated as having discontinued study treatment due to an adverse event on the end of treatment eCRF page.

Treatment-emergent bleeding events will be identified using standardized MedDRA queries (SMQs) by matching the event terms in SMQ "HAEMORRHAGES" and the first SMQ subcategory "HAEMORRHAGE TERM (EXCL LABORATORY TERMS)." The number of subjects with treatment-emergent bleeding events will be summarized for each treatment arm.

A listing of all adverse events will be provided.

5.2. Death

A summary of all deaths and cause of death will be tabulated by treatment arm. Specifically, the number of subjects who died during the study will be summarized for the all treated population. The primary cause of death collected on eCRF page will be reported.

A listing of death information will be provided.

5.3. Clinical Laboratory Tests

The evaluation of clinical laboratory tests will focus on the following selected laboratory analytes or events:

- Maximum post baseline CTCAE grade of hematological toxicity (anemia, leukemia, neutropenia, thrombocytopenia)
- Maximum post baseline CTCAE grade related to liver function test (ALT, AST, alkaline phosphatase, total bilirubin)
- Incidence of persistent (≥ 4 weeks) and severe (grade ≥ 3) cytopenia (thrombocytopenia/neutropenia)

The above analyses will be tabulated by treatment arm.

In addition, descriptive statistics (mean, SD, median, range) will be used to summarize observed laboratory values and change from baseline in observed value at each scheduled visit for each treatment arm.

Shift tables for each cycle will be produced as number of subjects with each baseline CTCAE grade and changes to the maximum CTCAE grade by analyte. Shift tables from baseline to worst value on treatment will also be provided.

All the lab data collected (hematology, chemistry, coagulation, urinalysis, and other lab tests) will be listed.

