3. PATIENT ELIGIBILITY

3.1. Inclusion Criteria

- Diagnosis of one of the following
 - Arms A, B, E, and F only: PMF per the revised World Health Organization (WHO) criteria ([Appendix B](#)),
 - Arms A, B, E, and F only: post-ET/PV MF per the IWG-MRT criteria ([Appendix C](#)).
 - Arm D only: Blast-phase MF defined as the presence of 20% or more blasts in the peripheral blood or bone marrow
 - Arm G only: MDS/MPN or MDS patients with spliceosome mutations including SF3B1, SRSF2 and U2AF1 mutations or ring sideroblasts. Diagnosis of MDS/MPN and MDS is per WHO criteria ([Tefferi and Vardiman 2008](#)). Direct sequencing will be used to confirm the presence or absence of spliceosome mutations.
- Indication for treatment of one of the following:
 - Arms A, B, E and F only: High-risk or Intermediate-2 risk MF (as defined by the Dynamic International Prognostic Scoring System [DIPSS-plus]; [Appendix A](#)).
 - Arm G only: presence of severe anemia defined as hemoglobin of <9 g/dL or other indications for cytoreductive therapy per physician discretion
- Presence of the following:
 - Arms E and G only: spliceosome mutations, including SF3B1, SRSF2 and U2AF1 mutations (by direct sequencing) or ring sideroblasts.
- Absence of the following:
 - Arm F only: spliceosome mutations (by direct sequencing) and ring sideroblasts
- ≥ 18 years of age with life expectancy of ≥ 12 weeks.
- Able to provide informed consent and be willing to sign an informed consent form.
- Eastern Cooperative Oncology Group (ECOG) performance status of 0, 1 or 2 ([Appendix D](#)).

- Evidence for acceptable organ function \leq 14 days of study registration as evidenced by the following:
 - SGOT (AST) \leq 2.5 x upper limit of normal (ULN) (or \leq 5 x ULN if in the investigator's opinion the elevation is due to extramedullary hematopoiesis)
 - SGPT (ALT) \leq 2.5 x upper limit of normal (ULN) (or \leq 5 x ULN if in the investigator's opinion the elevation is due to extramedullary hematopoiesis)
 - Total bilirubin \leq 3.0 mg/dL (or direct bilirubin $<$ 1 mg/dL).
 - Creatinine \leq 3.0 mg/dL.
 - Absolute neutrophil count \geq 1000/ μ L (this requirement not needed for Arm D).
 - Platelet count \geq 50,000/ μ L (this requirement not needed for Arm D).
- Females of childbearing potential must have a negative pregnancy test \leq 7 days prior to registration, unless they are surgically sterile (i.e., hysterectomy), OR postmenopausal (FSH $>$ 30 U/mL).

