SGOT (AST) and SGPT (ALT) ≥ Grade 3	Imetelstat	Hold imetelstat. Restart at the next lower dose level see Section 8.2), if recovered to Grade 1 or less (or to pre-study baseline).
Total Bilirubin >3.0 mg/dL (or direct bilirubin 1≥ mg/dL)	Imetelstat	Hold imetelstat. Restart at the next lower dose level (see Section 8.2), if recovered to Grade 1 or less (or to pre-study baseline).
Creatinine >3.0 mg/dL	Imetelstat	Hold imetelstat. Restart at the next lower dose level (see Section 8.2), if recovered to Grade 1 or less (or to pre-study baseline).

ADVERSE EVENT/ laboratory test abnormality (must be at least possibly related to drug to qualify as a dose-modifying event)	AGENT	ACTION ¹
Allergic Reaction Grade 2	Imetelstat	Hold imetelstat. Restart at the next lower dose level if adverse event reduced to \leq Grade 1. Discontinue imetelstat if event reoccurs at lower dose.
Allergic Reaction Grade 3	Imetelstat	Discontinue imetelstat and go to event monitoring per Section 4
Any Grade 3 ³	Imetelstat	Hold imetelstat. Restart at the next lower dose level (see Section 8.2), if adverse event reduces to \leq Grade 2.
Any Grade 4 ⁴		Hold imetelstat. Restart at the next lower dose level (see Section 8.2), if adverse event reduces to \leq Grade 2.

¹ Use the following to describe actions in the Action column:

- Omit = The current dose(s) for the specified drug(s) during a cycle is skipped. The patient does not make up the omitted dose(s) at a later time
- Hold/Delay = The current dose(s) of all drugs during a cycle is delayed. The patient does make up the delayed dose(s) when the patient meets the protocol criteria to restart drugs. Hold for maximum of 28 days, and then contact principal investigator and medical monitor.
- Discontinue = The specified drug(s) are totally stopped.

² Not required for cohort D.

³ Except fatigue, nausea, vomiting, diarrhea and hyperuricemia that persist despite treatment with optimal anti-diarrheals or anti-emetics. Such toxicity will be taken into account, for dose holding only when it persists despite appropriate treatment.

⁴ Except Grade 4 uric acid toxicity. Such toxicity will be taken into account for dose holding only when refractory to appropriate treatment.

In addition to any of the above toxicities, in the event of a drug-related Grade 2 or higher toxicity that the patient cannot tolerate or at the discretion of the Investigator, dosing may be reduced.

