10.3.1.10. Hepatic Adverse Events and Abnormal Liver Biochemistries

Abnormal liver biochemistries and hepatic AEs should be reported per routine protocol reporting procedures on the relevant eCRF (e.g., Adverse Event eCRF, chemistry CRF).

In the event a patient has discontinued imetelstat, but qualifies for the extended hepatic safety follow-up due to ongoing liver biochemistry abnormalities or hepatic AEs at the study

completion/early treatment termination visit, monitoring and data entry into the relevant eCRF (i.e., adverse event, laboratory data, and concomitant medications) should continue per the guidelines in [Table 4](#). These assessments should occur regardless of the initiation of alternate MF treatments.

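### SAP 5.3 counts persistent Grade 3 or worse cytopenia with no baseline condition and no window, so an Arm D patient who enters severely cytopenic and stays so can be tabulated as an incident case

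*SAP*

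**What the plan says.** SAP 5.3 lists three laboratory summaries. The first is "Maximum post baseline CTCAE grade of hematological toxicity", the second is the corresponding maximum for liver tests, and the third is "Incidence of persistent (≥ 4 weeks) and severe (grade ≥ 3) cytopenia (thrombocytopenia/neutropenia"). Of all three the SAP says "The above analyses will be tabulated by treatment arm", so Arm D has its own column. SAP 5 runs the safety analyses on all treated subjects.

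The same section also plans shift tables by cycle, adds that "Shift tables from baseline to worst value on treatment will also be provided", and plans a listing of all laboratory data.

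SAP 5.1 does set a window and a worsening rule, but only for adverse events. The window runs from first dose to 30 days after the last dose, or to subsequent anti-cancer therapy if that comes sooner. An event already present at baseline counts if it worsens or is later judged drug-related.

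Protocol 3.1 sets entry minimums for neutrophils (1000/µL) and platelets (50,000/µL), each with the note "this requirement not needed for Arm D". In Protocol 8.2, Table 11, the holds for low neutrophils and platelets carry a footnote: "Not required for cohort D".

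**The concern.** An incidence table in a safety report is normally read as what happened after the drug was started. The third item in SAP 5.3 does not ensure that reading. It lacks even the post-baseline qualifier that the first two items have, and that qualifier would not be enough: a patient who starts at Grade 3 and stays there has post-baseline values at Grade 3 too.

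Arm D is where this can matter most, because the protocol sets no floor on its entry counts. Myelosuppression is a central safety question here: Protocol 15.1.9 describes cytopenias as the main dose-limiting effect in Phase I, and Protocol 1.4.1 reports Grade 4 myelosuppression in a subset of this trial's patients. An Arm D rate that mixes disease present at entry with onset on treatment cannot be interpreted as toxicity.

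The missing window is a second, smaller gap that affects every arm.

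**Working it through.** The documents give no figure for this endpoint, so there is nothing to reproduce. The check is textual, followed by an illustration of size.

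**1. Does the definition exclude cytopenia present at entry?**

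| Element | Persistent cytopenia item (SAP 5.3) | Adverse events (SAP 5.1) |
|---|---|---|
| Baseline condition | none | a baseline event counts only if it worsens or is later judged drug-related |
| Start | none stated | first dose |
| End | none stated | 30 days after last dose, or subsequent therapy |
| Population | all treated | all treated |

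Read literally, the item does not exclude it.

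**2. Can such patients exist?** In Arm D, yes. With both minimums waived, any grade is possible at entry, whatever the CTCAE cut-offs are. In the other arms, whether the minimums keep patients below Grade 3 depends on cut-offs that the documents do not print. Those minimums are also checked at screening, which may be 14 days before registration, with treatment starting up to 7 days after it: 14 + 7 = 21 days before first dose. SAP 2.1 takes the last pre-dose value as baseline, and the all treated set includes ineligible subjects. The other arms are therefore less exposed, but not guaranteed to start at zero.

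**3. Do other outputs separate them?** The shift tables set baseline grade against maximum or worst grade. Neither form carries the four-week criterion, so a reader cannot tell which of the counted patients were already at Grade 3 or worse at baseline.

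**4. Size.** Let N be the patients in the arm, k those at Grade 3 or worse at baseline who stay there for four weeks, and q the new-onset rate among the other N − k.

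- Reported rate = (k + q(N − k))/N. Rate wanted = q.
- With no drug effect (q = 0), the reported rate is k/N, so each such patient adds 1/N: 1/11 = 9.1 points, 1/26 = 3.8 points.

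N = 11 and N = 26 are the planned stage 1 and full sizes for Arm D in Protocol 16.1. Its actual enrolment is not stated. Both k and q are assumptions.

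| N | k | q | Reported | Wanted |
|---|---|---|---|---|
| 11 | 0 | 10% | 10.0% | 10% |
| 11 | 1 | 10% | (1 + 1.0)/11 = 18.2% | 10% |
| 11 | 3 | 10% | (3 + 0.8)/11 = 34.5% | 10% |
| 26 | 3 | 10% | (3 + 2.3)/26 = 20.4% | 10% |
| 26 | 8 | 10% | (8 + 1.8)/26 = 37.7% | 10% |
| 26 | 13 | 10% | (13 + 1.3)/26 = 55.0% | 10% |
| 26 | 3 | 30% | (3 + 6.9)/26 = 38.1% | 30% |
| 26 | 13 | 30% | (13 + 3.9)/26 = 65.0% | 30% |

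With k = 0 there is no distortion.

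**5. Does the open window matter?** Protocol 4.1 continues monthly hepatic follow-up until resolution, and Protocol 10.3.1.10 says "These assessments should occur regardless of the initiation of alternate MF treatments". Blood counts taken then could fall inside an unbounded window while the patient is on another drug. Table 4 asks for a blood count only if total bilirubin is elevated, however, and persistence would normally need at least two low counts. This route is narrow.

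**The case against.** A reader might infer that the SAP counts Arm D's entry cytopenia as new toxicity. It does not say so. It is silent on the counting rule, and a programmer could take incidence to mean new onset. That stands: such patients can be counted, not are counted. But two competent programmers could produce different tables from the same text, which is reason enough to settle it.

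A reader might also quote an inflated rate for Arm D, such as 2/11 = 18% to 6/11 = 55% with no drug effect. The documents support no such range. They give neither baseline counts nor Arm D enrolment, and zero such patients is possible.

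The strongest defense is that baseline status is visible elsewhere. Arm D's cycle is 28 days, so the per-cycle shift tables come close to the four-week criterion, and the listing allows subject-level checks. This is partly right: the information is recoverable. But a maximum grade within a cycle does not show persistence, and a listing leaves each reader to rebuild the endpoint.

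The table's weight is also limited. The stopping rule in Protocol 16.8 uses non-hematologic events, the adverse event tables already have a window and a worsening rule, and Protocol 16.2 presents Arm D separately, so cross-arm comparison is not a planned use. All of this stands. It lowers the stakes without making the Arm D figure interpretable on its own.

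Finally, it is tempting to apply one cut-off to every item in SAP 5.3. That would remove extended hepatic follow-up from the liver table, and the protocol collects those data on purpose, after a clinical hold that concerned reversibility of hepatotoxicity (Protocol 1.3.4.4).

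**Conclusion.** The point holds as a gap in definition. With no baseline condition and no window, the persistent cytopenia item allows an Arm D patient who enters and remains at Grade 3 or worse to appear as an incident case, and no planned table separates such patients. The effect is 9.1 points per patient at n = 11 and 3.8 points at n = 26. The total is unknown and may be nil, because it depends on a number of patients that the documents do not give. The open window adds a minor further risk.

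The consequence is confined to a descriptive safety table, chiefly its Arm D column. The primary endpoint and the decision rules are untouched. The change is worth making because the figure could mislead and the repair is simple.

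The appearance of leukemia in the list of hematological toxicities ("anemia, leukemia, neutropenia, thrombocytopenia") looks like a slip for a white-cell term. It is an editorial matter and should not be read as a plan to grade leukemic transformation as a laboratory toxicity.

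**What to change.** In SAP 5.3:

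- For neutropenia and thrombocytopenia separately, count new persistent (four weeks or more) Grade 3 or worse cytopenia among patients with baseline Grade 2 or lower. Use those patients as the denominator and print it.
- Show patients with baseline Grade 3 or worse on a separate line, and note any who worsen from Grade 3 to Grade 4, in keeping with the third criterion of the treatment-emergent definition in SAP 5.1.
- Apply the SAP 5.1 window (first dose to 30 days after last dose, or subsequent anti-cancer therapy if earlier) to the two hematology items only.
- Leave the liver function table open to the extended hepatic follow-up.
- Replace leukemia with the intended white-cell term.

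The cost is a few lines of SAP text and one revised table definition, with no new data collection. The drawback is a smaller at-risk denominator in Arm D, and so a less precise rate there. The separate line keeps the remaining patients visible.

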5.4. Other Safety Tests

ECOG performance status, physical exam and infusion reaction will be listed separately by cycle.

REFERENCES

